# 3.2.3. Early Termination Visit

Subjects who do not reach a stable dose at Visits 3a-3d will proceed to the Early Termination Visit. Subjects who do not complete 2-weeks of PF-06412528 treatment at their maintenance dose for any reason will proceed to the Early Termination Visit.

All subjects who discontinue early from the study will complete the procedures specified for Visit 6/Early Termination (Section 6.3).

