# **SCHEDULE OF ACTIVITIES**

The Schedule of Activities table provides an overview of the protocol visits and procedures. Refer to STUDY PROCEDURES and ASSESSMENTS sections of the protocol for detailed information on each procedure and assessment required for compliance with the protocol.

The investigator may schedule visits (unplanned visits) in addition to those listed on the schedule of activities, in order to titrate study drug or conduct evaluations/assessments required to protect the wellbeing of the subject.

Periods		Screening	eening Treatment								
		(2 Wks)	Conversion/Titration Phase (1 to 4 Wks)					Ma	Follow Up//EOS (Clinic) (1 Wk)		
its	Visit	1	2	3a 	3b 	3c 	$3d^2$	4	5	6/ET	7
Scheduled Visits	Day ±Allowable Window	-14 to -1	1	7±2	NR	NR	NR	21±2	35±2	49±2	56±2
Inled					14±2	NR	NR	28±2	42±2	56±2	63±2
ched						21±2	NR	35±2	49±2	63±2	70±2
Š							28±2	42±2	56±2	70±2	77±2
	Activities										
Informed Consent/Assent 		X									
Inclus	sion/Exclusion Criteria (Sections 4.1 and 4.2)	X									
Demo	ographics	X									
Medi	cal History	X									
Opioi	d Therapy Review	$x^4$	$X^{5}$								
	Physical Examination (Section 7.2.6)	X								X	
	Clinical Laboratory Tests (Section 7.2.3)	X								X	
8.	Pregnancy Test (Section 7.3)	$X^{6}$	<				X 		>	$X^{6}$	
Safety	Urine Drug Test (Section 7.2.7)	X									
N	Single, 12–lead ECG  (Section 7.2.4)	X									
	Vital Signs (Section 7.2.2)	X	X	X	X	X	X	X	X	X	
	Suicide Ideation and Behavior (SIB)	X	X	X	X	X	X	X	X	X	X

Periods		Screening Treatment									Post-Treatment
		(2 Wks)	Conversion/Titration Phase (1 to 4 Wks)					Ma	Follow Up//EOS (Clinic) (1 Wk)		
its	Visit	1	2	3a 	3b 	3c 	3d 	4	5	6/ET	7
Scheduled Visits	Day ±Allowable Window	-14 to -1	1	7±2	NR	NR	NR	21±2	35±2	49±2	56±2
nled					14±2	NR	NR	28±2	42±2	56±2	63±2
pəq						21±2	NR	35±2	49±2	63±2	70±2
S							28±2	42±2	56±2	70±2	77±2
	Activities										
	Assessment (Section 7.4.1)										
	COWS (Section 7.2.5)	X	X	X	X	X	X	X	X	X	
	Concomitant Medication (Section 5.7)	X	X	X	X	X	X	X	X	X	
	Adverse Events  (Section 7.2.1)	X	X	X	X	X	X	X	X	X	X
	Pain Intensity (In-Clinic) (Section 7.1.1)		X	X	X	X	X	X	X	X	
Treatment Response	Review Diary Information 11			X	X	X	X	X	X	X	
odsa	Pain Intensity (Diary Review)			X	X	X	X	X	X	X	
t Re	Rescue Medication (Diary Review)			X	X	X	X	X	X	X	

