# 3.2.1. Conversion/Titration Phase (Visits 2-3d)

Subjects and their caregiver(s) will report for weekly visits during this 1-4 week period to convert their current standard of care opioid therapy for pain management to PF-06412528. The goals of the Conversion/Titration Phase are to convert subjects from their pre-study standard of care opioid analgesic to PF-06412528 and to individualize pain management by titrating PF-06412528 (Visits 2-3d; see Schedule of Activities) to achieve a stable dose. A stable dose is characterized as a dose that provides adequate analgesia and minimizes adverse reactions for 5 to 7 days. During Visit 2 the subject's study eligibility will be verified, the subject's current standard of care opioid therapy will be discontinued and PF-06412528 will be initiated at a dose determined using the PF-06412528 Conversion Guide (Appendix 2).

Four weekly scheduled study visits (Visits 3a-3d) are planned to provide enough time to individualize pain management with PF-06412528. Visit 3a is mandatory for all subjects and Visits 3b, 3c, and 3d are optional, if additional dose titration is needed. Visits 3b or 3c or 3d can be skipped if a subject reaches a stable dose at a prior visit. When a stable dose is achieved, the subject advances to the Maintenance Phase at the next visit (Visit 4). More frequent consultation with the investigator as well as additional unscheduled clinic visits are permitted, as needed (eg, to titrate study drug). All information about the dosing of PF-06412528 (ie, dosage strength, frequency of dosing, and daily schedule) will be obtained and recorded at each scheduled/unscheduled visit.

The Conversion/Titration Phase will end once a PF-06412528 dose that provides adequate analgesia and minimizes adverse reactions is achieved (ie, stable dose) with infrequent need for IR morphine as rescue as determined by the investigator. Subjects who do not reach a stable dose without the need for IR morphine as rescue by Visit 3d, will be removed from treatment and converted back to their previous opioid therapy or another therapy at the discretion of the investigator.

The start of the Maintenance Phase will begin once a subject has achieved a stable dose of PF-06412528 and the next study visit (Visit 4) will be scheduled in two weeks' time.

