# 3.2.2. Maintenance Phase (Visit 4-6)

The goal of the Maintenance Phase is to characterize the PK under steady-state study conditions as well as demonstrate the safety of PF-06412528 over a 2-6 week period. If at Visit 4 subjects require additional pain relief in the opinion of the investigator, they will continue in the study for an additional 2-4 weeks (Visit 5 and/or Visit 6) up to 6 weeks total.

Daily Diary and in-clinic pain intensity and safety will be assessed at each visit to determine if any dose adjustments are required. Rescue medication (acetaminophen and/or NSAID's) is permitted during this phase. IR morphine for rescue is discouraged during the Maintenance Phase.

Blood samples will be collected for PK analysis at Visit 4 for those subjects that achieve a stable dose between Visits 3a-d. Two blood samples will be taken at least two-hours apart at Visit 4. If for any reason PK samples are not obtained at Visit 4, the subject should return to enable them to be obtained at an unscheduled visit.

At the final Maintenance Phase visit (Visit 4 or 5 or 6), the investigator will discontinue the subject's PF-06412528 therapy and convert the subject back to their standard of care of opioid therapy. Blood samples will be collected for PK analysis if not already obtained. A Post-Treatment/End of Study visit will be scheduled in 7 ±2 days (Visit 7).

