# 3.3. Post-Treatment Period/End of Study Period

The purpose of the Post-Treatment Period/End of Study (Visit 7) is to perform safety assessments  $7 \pm 2$  days after the last dose of PF-06412528 at Visit 6.

Subjects who discontinue early from the study as well as subjects who complete 2 weeks of PF-06412528 during the Maintenance Phase and have their last dose of PF-06412528 at Visit 4 will complete the Visit 6/Early Termination procedures without the need to return for the Post Treatment/End of Study Visit.

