# • Assess Treatment Response:

- Pain intensity (Diary Review and in-clinic assessment);
- Rescue Medication (Diary Review);
- Concomitant Medication (Diary Review);
- Study Drug Use (Diary Review);
- Adverse Events (Diary Review).
- COWS Assessment.
- Concomitant Medication Assessment.
- Adverse Event Assessment.
- **Pregnancy Test:** Take a urine sample from all females of childbearing potential.
- **Vital Signs:** Record blood pressure, pulse rate, and respiration.
- SIB Assessment: C-SSRS (Section 7.4.1):
  - Children's Since Last Visit (Ages 7-11) (Version 6/23/10)-(Appendix 5).
  - Since Last Visit (Ages 12-17) (Version 1/14/09)-(Appendix 6).
- Drug Accountability: See Section 5.6.
- **Dose Titration:** Adjust PF-06412528 dosage as needed to optimize pain therapy.
- **Prescribe Rescue Medication (if needed):** Prescribe rescue medication (acetaminophen and/or NSAID's) to be used during conversion and titration.
- **Dispense Study Drug** (PF-06412528) to caregiver.

**For Converted Subjects:** If, at this visit, the subject has been fully discontinued from the standard of care opiate therapy and successfully titrated to a stable dose of PF-06412528 and with infrequent use of IR morphine for rescue the subject may be scheduled for the next visit, which will be Visit 4 (Schedule of Activities). It is at this visit (Visit 3a) the subject enters the Maintenance Phase of the Treatment Period.

**For Non-Converted Subjects:** If, at this visit, the subject **has not** achieved a stable dose of PF-06412528, this subject will remain in the Conversion/Titration Phase, therefore:

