#### 6.2.2. Maintenance Phase

Once the investigator has determined that the subject has achieved a stable dose of PF-06412528, the subject will enter the Maintenance Phase of the Treatment Period and scheduled to return in two weeks for Visit 4. In the event a subject prematurely withdraws before Visit 4, perform the Visit 6/ET procedures a soon as possible.

### Visit 4

Perform the following assessments:

- Follow the same procedures and assessments as described at Visit 3a.
- Obtain Plasma Samples: Obtain 2 separate 6 mL blood samples for measurement of the concentration of morphine and metabolites in plasma and naltrexone and 6-β-naltrexone in plasma, with at least 2 hours separating the 1st and 2nd samples.

Record the following items on the appropriate CRF:

- The exact dosing date and clock times of the morning dose and previous 3 doses of PF-06412528, and
- The exact clock time of the blood draw for the 2 samples.

### Visit 5

• Follow the same procedures and assessments as described at Visit 3a.

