# 9.1. Sample Size Determination

The study plans to enroll approximately 140 subjects for the purpose of establishing a safety database, with at least 100 subjects exposed to at least 2 weeks of the Maintenance Phase with neither age group exceeding a 3:1 margin compared to the other age group (7-11 years old and 12-17 years old).

CC

CCI

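### Treatment may end at Visit 4, whose window opens before 2 weeks of Maintenance are complete, and nothing keeps a child on drug until the 2 weeks counted in Section 9.1 are reached

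*Protocol*

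**What the plan says.** **Target.** Protocol 9.1 plans about 140 enrolled, with "at least 100 subjects exposed to at least 2 weeks of the Maintenance Phase". The Document History gives FDA advice as the origin of this minimum.

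**Start of the clock.** Protocol 6.2.1, on a child found stable at Visit 3a: "It is at this visit (Visit 3a) the subject enters the Maintenance Phase of the Treatment Period". Visits 3b, 3c and 3d have the same rule.

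**Timing of Visit 4.** Protocol 6.2.2 has the child "scheduled to return in two weeks for Visit 4", and 3.2.1 also sets two weeks. In the Schedule of Activities, the row "Day ±Allowable Window" places both visits by study day, each ±2: Visit 3a at Day 7 and Visit 4 at Day 21, with the pairs 14/28, 21/35 and 28/42 for later entry.

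**Stopping.** Protocol 3.2.2: "At the final Maintenance Phase visit (Visit 4 or 5 or 6), the investigator will discontinue the subject's PF-06412528 therapy". The stated ground for going on past Visit 4 is the investigator's view that more pain relief is needed. Days on drug play no part.

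**Short exposure.** Protocol 3.2.3: "Subjects who do not complete 2-weeks of PF-06412528 treatment at their maintenance dose for any reason will proceed to the Early Termination Visit". Section 6.3 repeats this. Section 3.3 says that children who complete 2 weeks in Maintenance and "have their last dose of PF-06412528 at Visit 4 will complete the Visit 6/Early Termination procedures" need not return for Visit 7. None of these sections turns 2 weeks into a number of days.

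**SAP.** Section 2.1 sets the target as 100 completing the Maintenance Phase, described as lasting 6 weeks. Section 8.1.10 summarises duration of exposure by phase and names no count at 2 weeks.

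**The concern.** The target is a minimum, but the visit at which treatment may end is centred on that minimum with equal room on both sides. An early but in-window Visit 4 therefore falls below it. A child who is comfortable at such a visit may be stopped and converted back to standard of care with no deviation from the schedule. The Early Termination rule then says which visit the child attends; it does not keep the child on drug. On a strict reading of 9.1 that child is lost from the 100. Because no day count or tolerance is given, another reader could count the same child.

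At stake is the study's stated size. Exposure can be tabulated later at any cut-off, but drug days not taken cannot be added after conversion back.

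**Working it through.** **1. The plan's own interval.** From the Schedule: 21 − 7 = 28 − 14 = 35 − 21 = 42 − 28 = 14 days. This reproduces the two weeks of 3.2.1 and 6.2.2.

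**2. Range allowed.**
- Booked from the actual entry date, ±2 on Visit 4 only: 14 − 2 = 12 to 14 + 2 = 16 days.
- Both visits by study day: 19 − 9 = 10 to 23 − 5 = 18 days, and the same for the other three pairs.

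One sentence of 3.2.1 can be read as placing Maintenance entry at Visit 4. That cannot be meant: a child stopped at Visit 4 would then have no Maintenance time, yet 3.3 describes such a child as having completed 2 weeks.

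**3. Who can fall short.** Only children stopped at Visit 4. A child who goes on to Visit 5 has at least 33 − 9 = 24 days.

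**4. Day count used here.** Counting first and last day, days = gap + 1. Fourteen days then needs a gap of 13 or more, so gaps of 10 to 12 fall short.

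**5. Share of Visit 4 stoppers falling short (s).** The documents give no visit timing, so these are assumptions.
- All visits exactly on day: 0%.
- 60% on day and 10% on each other window day. Visit 4 only: gap 12 has probability 10%. Both visits, independent: gap 12 = 0.06 + 0.01 + 0.06 = 0.13, gap 11 = 0.02, gap 10 = 0.01; total 16%.
- Uniform over the window. Visit 4 only: 1/5 = 20%. Both visits: gaps 10, 11 and 12 arise from 1 + 2 + 3 = 6 of 25 combinations, 24%.

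**6. Effect on the 140.** Assume that half of those reaching Visit 4 stop there (this share is also not in the documents). To keep 100 qualifying, 100/(1 − 0.5s) must reach Visit 4, rounded up.

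| Timing | s | Needed at Visit 4 | Left of 140 for earlier losses |
|---|---|---|---|
| All on day | 0% | 100 | 40 (29%) |
| 60% on day, Visit 4 only | 10% | 100/0.95 → 106 | 34 (24%) |
| 60% on day, both visits | 16% | 100/0.92 → 109 | 31 (22%) |
| Uniform, Visit 4 only | 20% | 100/0.90 → 112 | 28 (20%) |
| Uniform, both visits | 24% | 100/0.88 → 114 | 26 (19%) |

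**7. Supply (Protocol 5.3.1, Maintenance bottles).** BID: 36/2 = 18 days. 2x20 mg BID: 72/4 = 18 days. 15 mg QD: 18/1 = 18 days. 10 mg QD: 20/1 = 20 days.

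**The case against.** **Visit 4 is meant to be two weeks after entry.** Sections 3.2.1 and 6.2.2 say so, and gaps of 10 or 11 days sit poorly with them. This stands: 12 to 16 days is the better reading, and with both end days counted only a 12-day gap then fails. The low end is still below the minimum.

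**The Early Termination rule can be met anyway.** Section 3.2.3 counts time at the maintenance dose, and 3.2.1 defines a stable dose by 5 to 7 days of adequate analgesia with minimal adverse reactions. A child confirmed stable may already have 5 days at that dose, so even a 10-day gap gives about 15 days. This stands for that sentence. It does not help with 9.1, which counts the phase, and it shows that the two rules can disagree about the same child.

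**Section 3.3 treats a planned Visit 4 stop as following 2 weeks.** It shows the intention, but it does not hold Visit 4, or the last dose, back until 2 weeks have passed.

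**The consequence is limited.** The 140 is approximate and serves to obtain 100, and dosing is recorded daily and transcribed to the CRF (5.2). Both points stand. The sponsor can count at any cut-off and enrol more children, but it cannot recover the children already stopped.

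**Stronger readings that the documents do not support.**
- A reader might require 14 elapsed days. Uniform windows would then give 10/25 = 40% short, 100/(1 − 0.5 × 0.40) = 125 needed at Visit 4 and 140 − 125 = 15 left. The documents do not define 2 weeks as elapsed days, and a 13-day gap passes when both end days count.
- A reader might infer from SAP 2.1 that every Visit 4 stopper fails the target. That SAP describes the design before Amendment 2 (chronic pain, a Visit 8, a 6-week Maintenance Phase) and has no planned stop at Visit 4. It needs updating; it is not a rival definition of 2 weeks.

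**Conclusion.** The point holds and should be corrected. A symmetric window centred on a required minimum, combined with permission to stop at that visit, lets a child leave treatment in window without the exposure that 9.1 counts.

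Its size is uncertain. The documents give neither visit timing nor the share stopping at Visit 4. With both end days counted, the illustrative shortfall among Visit 4 stoppers runs from 0% to 24%. With half stopping there, the allowance for earlier losses falls from 40 to between 26 and 34 of 140 in the non-zero cases. A reader might infer that the target will be missed; the documents do not show that, because the shortfall is nil if visits are kept on day. Nor do the safety results change: the safety set, PK samples and adverse-event tables are the same either way.

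**What to change.** 1. **Visit 4 timing.** Count the window from the actual Maintenance-entry date and make it one-sided, for example 0/+3 days (14 to 17 days). The 18-day bottles then keep about one day in reserve (18 − 17 = 1). Count Visits 5 and 6 from the same date, so that a later Visit 4 does not crowd them. Alternatively, keep the window and state that drug is not stopped at Visit 4 before day 14 of Maintenance.

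2. **One definition.** In Protocol 9.1, 3.2.3 and 6.3, define 2 weeks as 14 days or more from the visit confirming the stable dose (3a to 3d) to the last dose, both days counted, regardless of dose adjustment.

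3. **SAP consistency.** Align the SAP 2.1 target with 9.1 and report n (%) meeting it, overall and by age group, since the 3:1 margin in 9.1 refers to these children.

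**Cost.** No added visit, sample or assessment, and no change in bottle fill. A child may take up to 17 − 16 = 1 more day of study drug than under the present +2 window counted from entry. Sites lose the option of an early Visit 4, and the window has 4 permitted days instead of 5.

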# 3.3. Post-Treatment Period/End of Study Period

The purpose of the Post-Treatment Period/End of Study (Visit 7) is to perform safety assessments  $7 \pm 2$  days after the last dose of PF-06412528 at Visit 6.

Subjects who discontinue early from the study as well as subjects who complete 2 weeks of PF-06412528 during the Maintenance Phase and have their last dose of PF-06412528 at Visit 4 will complete the Visit 6/Early Termination procedures without the need to return for the Post Treatment/End of Study Visit.

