### Visit 3d (Day $28 \pm 2$ days)

• Follow the same procedures and assessments as described at Visit 3a.

**For Converted Subjects:** If, at this visit, the subject has been fully discontinued from the standard of care opiate therapy and successfully titrated to a stable dose of PF-06412528 and with infrequent use of IR morphine for rescue the subject may be scheduled for the next visit, which will be Visit 4 (Schedule of Activities). It is at this visit (Visit 3d) subject enters the Maintenance Phase of the Treatment Period

**For Non-Converted Subjects:** If, at this visit, the subject **has not** achieved a stable dose of PF-06412528, the subject will be discontinued from treatment. PF-06412528 will be discontinued and if needed, converted to a standard of care analgesic therapy at the investigator's discretion.

- Schedule the Visit 6/Early Termination Visit: See Section 6.3.
- Schedule the Post Treatment/End of Study (Visit 7): See Section 6.4.

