#### Visit 6/Early Termination

During this visit the following procedures will be followed for all subjects:

- Physical examination.
- Serum pregnancy test.
- Clinical Laboratory Test (Hematology, blood chemistry and urinalysis): See Section 7.2.3.
- Follow the same procedures and assessments as described at Visit 3a, (except do not perform the urine pregnancy test, instead a serum pregnancy test should be performed at this visit): See Schedule of Activity and Section 7.3.

- Obtain plasma samples for PK analysis (only if not acquired at Visit 4): Record the following items on the appropriate CRF:
  - The exact dosing date and clock time for the morning and previous 3 doses of PF-06412528, and
  - The exact clock time of the blood draw for the 2 samples.
- Subjects who discontinue early from the study as well as subjects who complete 2 weeks of PF-06412528 during the Maintenance Phase and have their last dose of PF-06412528 at Visit 4 will complete the Visit 6/Early Termination procedures without the need to return for the Post Treatment/End of Study Visit.
- Schedule Post Treatment/End of Study Visit, if required.

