# **6.3. Early Termination Visit**

Subjects who do not reach a stable dose at Visits 3a-3d will proceed to the Early Termination Visit. Subjects who do not complete 2-weeks of the PF-06412528 treatment at their maintenance dose for any reason will proceed to the Early Termination Visit.

All subjects including subjects who discontinue early from the study will complete the procedures specified for Visit 6/Early Termination (see Section 6.2.2).

### 6.4. Post Treatment/End of Study (EOS) Visit 7

Approximately 1 week after discontinuing PF-06412528 and initiating dose conversion back to the subject's standard of care therapy, subjects will undergo the Post-Treatment/End of Study procedures, which will consist of an assessment of any **AEs** since the previous visit and the **suicidality assessment**.

The following procedures will include:

- SIB Assessment: C-SSRS (Section 7.4).
- AE assessment.

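### Protocol sections disagree on who has post-treatment Visit 7; separately, the 8.2 CRF bullet ends SAE recording early and the AE tables count post-dose events under Maintenance

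*Protocol*

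**What the plan says.** **Who has Visit 7**

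- Protocol 3.3 places Visit 7 at 7 ±2 "days after the last dose of PF-06412528 at Visit 6". It then says that early discontinuers, and subjects who complete two Maintenance weeks with their last dose at Visit 4, "will complete the Visit 6/Early Termination procedures without the need to return for the Post Treatment/End of Study Visit".
- Protocol 6.2.2, Visit 6/Early Termination, repeats the exemption for early discontinuers and for subjects who "have their last dose of PF-06412528 at Visit 4 will complete the Visit 6/Early Termination procedures without the need to return", and adds "Schedule Post Treatment/End of Study Visit, if required".
- Protocol 3.2.2: "At the final Maintenance Phase visit (Visit 4 or 5 or 6), the investigator will discontinue the subject's PF-06412528 therapy". The same paragraph continues: "A Post-Treatment/End of Study visit will be scheduled in 7 ±2 days (Visit 7".
- Protocol 6.2.1, Visit 3d, non-converted subjects: "Schedule the Post Treatment/End of Study (Visit 7". This stands next to the instruction to schedule the Early Termination visit.
- Protocol 6.4 gives the content of Visit 7: "subjects will undergo the Post-Treatment/End of Study procedures, which will consist of an assessment of any" AEs since the previous visit, together with the C-SSRS.
- SAP 2.1 still describes an older design with a Visit 8 at 28 days. It requires Visit 7 of every treated subject, early stoppers included.

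**When AE recording ends**

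- Protocol 7.2.1.1 enters AEs on the CRF until the End of Study requirements are complete, and SAEs from consent to 28 days after the last dose.
- The bullet closing Protocol 8.2 enters serious and non-serious AEs alike from first dose through the last visit. The paragraph above it sets SAE reporting to the sponsor at 28 days after the last dose.

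**Where AEs are tabulated**

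- Protocol 9.4.1 and SAP 8.1.4 give treatment-emergent AEs a start but no end in the definition. They use two columns, Conversion/Titration and Maintenance, and the second extends to End of Study.
- The primary safety endpoint (Protocol 2.2.1, SAP 6.1.1) is AEs while on PF-06412528.

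**The concern.** The study exists to build a safety database, and Visit 7 is its one scheduled post-dose look at AEs and suicidality. Two kinds of child are excused from it in one place and booked for it in another: those who finish at Visit 4 and those who never reach a stable dose. A site that follows the text as written can go either way, so scheduled capture of non-serious AEs and the C-SSRS after the last dose can depend on the site and on how the child finished.

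Two further matters stand on their own. A site that works from the 8.2 bullet could close SAE entry on the CRF well before a site that works from 7.2.1.1. And because the child is switched back to standard-of-care opioid at the final visit, an event starting after that switch is counted in the Maintenance column although the drug has been stopped.

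**Working it through.** **1. Reproduce the plan's own Visit 7 days.** The Schedule of Activities has the stable dose reached on Day 7, 14, 21 or 28, with Visits 4, 5 and 6 at +14, +28 and +42 days. Visit 7 is last dose + 7.

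- Last dose at Visit 6: 7+42+7 = 56, then 63, 70 and 77. This matches the Schedule exactly.
- Last dose at Visit 5: 7+28+7 = 42, then 49, 56 and 63.
- Last dose at Visit 4: 7+14+7 = 28, then 35, 42 and 49.

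The Schedule gives Visit 7 days only for the Visit 6 path.

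**2. Set the sections side by side.**

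| Subject | 3.3 and 6.2.2 | Other current protocol text | SAP 2.1 |
|---|---|---|---|
| Finishes at Visit 4 | Excused | 3.2.2 schedules Visit 7 | Required |
| Not converted at Visit 3d (sent to Early Termination by 3.2.3 and 6.3) | Excused | 6.2.1 schedules Visit 7 | Required |
| Other early stopper | Excused | No section schedules it for this group by name | Required |
| Finishes at Visit 5 | Not mentioned | 3.2.2 schedules Visit 7 | Required |
| Finishes at Visit 6 | Scheduled | 3.2.2 schedules Visit 7 | Required |

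The first two rows are contradictions within the current protocol.

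**3. Scheduled post-dose observation.**

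- Visit 7 attender: 7−2 = 5 to 7+2 = 9 days.
- Excused Visit 4 finisher: d days, where d is the delay from last dose to the Visit 6/ET procedures. The documents do not give d; it is 0 if they are done on the last-dose day.
- Excused early stopper: the interval to the Early Termination visit, which is to take place as soon as possible but has no stated limit.

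**4. SAE entry on the CRF, 8.2 bullet against 7.2.1.1.** This takes the bullet to mean each subject's own last visit.

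- Visit 7 attender: 28−9 = 19 to 28−5 = 23 days short.
- Excused Visit 4 finisher: 28−d days short, so 28 if d = 0.
- The start differs too: first dose in the bullet, consent in 7.2.1.1.
- For non-serious AEs, the last visit and the completion of End of Study requirements nearly coincide when Visit 7 takes place. They can part when it is waived.

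**5. How many subjects.** The documents do not say. As an illustration, assume that all 140 enrolled are treated, that exactly 100 reach two Maintenance weeks (Protocol 9.1), and that a share f of those 100 stop at Visit 4. The share excused under 3.3 is (140−100+100f)/140: 40/140 = 28.6% at f = 0, 90/140 = 64.3% at f = 0.5, and 100% at f = 1. This is a range, not a forecast.

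**6. AE tables.** An AE that starts after the last dose goes under Maintenance if the subject entered that phase. If the subject never did, neither document says where it goes. Onset date and time are collected (7.2.1.1), so the split can be made from the data.

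**The case against.** Several passages that look like further conflicts are not, and this much of the other side stands:

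- A reader might infer that Visit 5 finishers have no rule. Section 3.2.2 covers them; 3.3 merely omits them.
- The C-SSRS requirement in 7.4.1 applies to scheduled visits, and a child excused from Visit 7 has none. Section 6.4 lists procedures, and 6.5 refers back to the protocol's follow-up. The conditional scheduling line in 6.2.2 agrees with the exemption above it. The Schedule calls itself an overview.
- SAP 2.1 describes a superseded design, so it is a mismatch to update rather than independent proof.
- The exemption is permissive; a site may still book Visit 7.
- A reader might infer that SAEs will be lost. The documents do not support that: sponsor reporting runs 28 days in 8.2, and Schedule note 10 agrees.
- Other routes may pick up events: the best-effort 28-day AE and suicidality contact in 6.5, the weekly caregiver calls (Schedule notes 11 and 16; 7.2.1.2) and the Post-Treatment diary (4.4 and 6). The documents do not say whether the calls and diary continue for excused subjects, and the 28-day contact sits in the withdrawal section.
- A reader might infer that the table layout makes capture differ between sites. It cannot; it only blurs what was captured.

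The argument that a specific rule overrides a general one does not remove the core. Section 3.2.2 names Visit 4 as a possible final visit, and the Visit 3d text names one particular group of early stoppers.

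**Conclusion.** The concern holds, as three separate points of modest size.

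1. Current protocol text both excuses and schedules Visit 7 for Visit 4 finishers and for non-converters. For the same kind of child, scheduled post-dose AE and C-SSRS follow-up is 5 to 9 days on one reading. On the other it is about 0 days for a Visit 4 finisher, assuming same-day exit procedures, or an unspecified interval for an early stopper.
2. The 8.2 bullet, read literally, stops SAE entry on the CRF 19 to 23 days before the 7.2.1.1 limit for attenders, and about 28 days before it for an excused Visit 4 finisher under the same assumption. These figures measure a difference in wording, not expected data loss.
3. The AE tables mix on-drug and post-dose events under Maintenance and give no place to post-dose events of subjects who never entered that phase.

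What is at risk is mainly non-serious AEs, the C-SSRS and SAE entry on the CRF. The analysis is descriptive and the primary endpoint concerns time on drug, which limits the consequence. The number of subjects affected cannot be derived from the documents. This should be fixed, but it does not undermine the study.

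**What to change.** - Reconcile Protocol 3.2.2 and 6.2.1 (Visit 3d) with 3.3 and 6.2.2 into one rule on who has Visit 7, timed from the last dose, and update SAP 2.1 to match. This review takes no position on which rule it should be.
- Align the CRF bullet in 8.2 with 7.2.1.1 for SAEs.
- In Protocol 9.4.1 and SAP 8.1.4, use the recorded onset dates to tabulate AEs that start after the last dose separately from on-treatment AEs, including those of subjects who never entered Maintenance.

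The cost is text edits, a SAP update and one extra column in the AE tables.
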